During COVID, we will have the option to complete a modified initial evaluation if the participant is not allowed to leave TRISL, as indicated by the circumstances (e.g. number of cases in the community, orders issued by the Health Department, or current policies at The Rehabilitation Institute of St. Louis). After the participant consents, the study therapist will use the "Participant Intake Form" to gather information from the TRISL therapists about the current level of functioning of the participant as well as the participant's concerns about going home. The study therapist will then arrange with a family member or friend to meet at the participant's home to complete the modified home visit. During the home visit, the therapist will complete a home safety assessment to evaluate the home environment and will also look specifically at the six therapist priority activities from the I-HOPE (getting in/out house, moving around the house, getting on/off toilet, getting in/out of the shower, getting on/off toilet, and getting in/out of the bed) and identify environmental barriers that will impede the participant's performance of those activities. The therapist will take pictures of the home, including the areas where the six therapist priority activities occur. After the modified home visit is completed, the study

therapist will review the home evaluation with the participant and will share the results of the evaluation with the TRISL therapist team.

If the home evaluation is completed during COVID using the procedures described above, the therapist will meet with the study participants in the treatment group before they discharge from TRISL and review recommendations for home modifications and adaptive equipment. The therapist will facilitate implementing the agreed upon modifications/adaptive equipment prior to discharge from IR following normal study procedures.

Randomization and Blinding

Age is a negative marker for functional recovery after stroke, and functional status is a strong predictor of recovery.^{61,62} The Functional Independence Measure (FIM) will be used to determine functional status post-stroke. Randomization will be balanced using the participant's age and FIM score.

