Participants will be allocated using a 1:1 ratio via adapted randomization sequences generated *a priori* by the study statistician, [name], using a computerized formal probability model. The allocation ratio will be maintained at periodic intervals. Randomization sequence concealment will be achieved by query of the REDCap (Research Electronic Data Capture) system.⁶³ After baseline assessment (T1) is securely uploaded and locked and stratification variables are entered, the interventionist will elicit the treatment assignment in the field in real time using a secure data connection to REDCap. This will permit prioritization of problems for participants assigned to the treatment group.

Upon randomization, participants will be assigned to an interventionist by the treatment coordinator. Although the results of the home assessments will be shared with the rehabilitation staff, IR staff will be blinded to the group placement so that they do not modify their inpatient or discharge treatment plan. All outcomes will be assessed by a blinded rater.

Phone Assessment T1b

To allow time for participants to adjust and personally assess their participation, T1 participation assessments will be conducted for both groups by telephone 2 days after discharge from IR. A rater who is blinded to allocation will conduct the baseline assessment for the primary, secondary, and exploratory endpoints.

Upon completion of T1b phone assessment, the participant will receive visits 2–6 over an 8-week period. The home modification group will progress from daily activity performance to community participation.

Primary Intervention

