NIH Toolbox Instrumental Support Scale measures the availability of support for an individual to assist with completing daily tasks; 8-item scale, uses a 5-point likert scale response, scores are summed with higher score indicating more instrumental support.

10-Item Connor-Davidson Resilience Scale will measure resilience or ability to adjust to a stressful situation; consists of 10 items, all answered used a 5-point likert scale; total scores range from 0-40, with higher scores indicating greater resilience.

Healthcare Utilization and Mortality

Retrospective review of the medical records of all randomized participants to collect date of death, hospitalizations, emergency room visits, and skilled nursing facility (SNF)/Inpatient Rehabilitation (IPR) admissions between participants' date of enrollment until date of final study contact as a follow up metric to identify patient outcomes (see waiver of consent).

Statistical Analyses

Intention-to-Treat Analysis

We will perform our analyses using an intention-to-treat paradigm. We will perform exploratory data analysis looking for extreme or otherwise unusual values. Non-normal and heteroscedastic data will be transformed as necessary.

Baseline Analyses

We will use unpaired *t* tests and chi-square tests to compare T0 and baseline characteristics in the two groups for descriptive information (except when statistical assumptions are not met, in which case we may use Wilcoxon or Fisher exact tests).

Missing Data

We expect missing values in outcome measures because of dropout, death, missed assessment, or nonresponse. Our main analysis, a linear mixed-effects model, accommodates missingness due to treatment, prior outcome, or baseline covariates missing at random.⁸² Assuming that missing data occur at random, inferences will be valid even if we have differential dropout by intervention arm. If the missing data mechanism is not ignorable (ie, missing is not at random), then mixed-effects selection models or pattern-mixture models will be used.⁸³

Primary Analysis

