Our primary analysis (testing primary hypothesis) will be based on a linear mixed model using baseline and 12-month RNLI s, accounting for the correlation between a participant's repeated measurements over time. The fixed-effect portion of the model will have the form $Y_{it} = \beta_0 + \beta_1 \times 12\text{ months} + \beta_2\text{Group} + \beta_3\text{Group} \times 12\text{month}$, in which Y_{it} is the RNLI score for participant i at baseline (time 0) and 12 months (time 1), and *Group* indicates study arm. In this model, the baseline RNLI is modeled as a dependent variable.²⁷ For improved precision, the model will be adjusted for baseline covariates including race, sex, depression, and length of hospital stay if an imbalance in covariates between arms is observed in baseline analyses. In this model, β_0 is the mean RNLI score for the control arm at time 0, and β_1 is the change in the mean RNLI from baseline to time 1 for the control

arm; β_2 is the mean RNLI score for the treatment arm at time 0, and β_3 is the change in mean RNLI from time 0 to time 1 for the treatment arm. The primary hypothesis is that the difference in the change in RNLI scores from time 0 to time 1 between arms will be tested by examining β_3 , which estimates the difference.

Secondary Analyses

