For the secondary analyses of the change in SIS score at 1 year and the change in I-HOPE at 1 year, we will use the same approach as for the primary analysis because these two outcomes are also continuous. We have overall type I error control for testing the 1-year change in these three analyses at the design stage. The significance level for testing is 0.016. In addition to comparison of 1-year change, we will extend the model by including scores immediately after intervention and at 6 months to see whether the difference in outcomes is achieved at those time points. Depending on the form of time variable in the model, we will use appropriate regression coefficients or a linear combination of the regression coefficients to determine the difference in change of these scores between arms at certain time points. Interpretation of these results should be cautious because we do not have the type I error controlled for these analyses. Because it is possible that severity of functional impairment after stroke may impact response to treatment, we will analyze impact of functional impairment on response to treatment. We will examine functional impairment by group interaction to examine possible differential intervention effects of functional impairment on community participation and performance of daily activities.

Safety

To determine whether the intervention poses no greater risk than AC, we will examine the differences in numbers of falls and rehospitalizations between groups. The statistical models for count data will be used for analyses of these two outcomes. Using the number of falls as an example, we will fit a Poisson regression model (with overdispersion adjustment if necessary), in which a dummy variable for the intervention arm is used. The regression parameter estimate for this dummy variable is the log of rate ratio of falls for COMPASS versus control arm, and exponentiation of the regression parameter estimate is rate ratio. Using the parameter estimate and its standard error, we can construct a two-sided 95% CI for the rate ratio. We expect the confidence interval for rate ratio will include 1, indicating no significant difference in the fall rate between the two groups.

Process Outcomes

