Evaluate acceptability and feasibility to aid in the interpretability of the trial. COMPASS will have high acceptability (80% retention), high fidelity by therapists (95% of elements and 90% of dose delivered), low safety risk (no increased rate of falls or health care use compared with the AC group), and high adherence (80% of modifications in use) at 12 months. We will conduct between-group comparisons of process endpoints collected at each time point (time to first fall, number of injurious falls, health care utilization rate, dosage delivered, and adherence rate) using unpaired *t* tests or chi-square tests. We will compare the characteristics of patients who complete the assigned intervention with those who do not for differences in stroke severity and comorbidities. Descriptive statistics will be used for costs per participant and adherence.

Sample Size Calculations

The study is designed to have 80% of power to reject three null hypotheses of equal mean changes in the primary and secondary endpoints (RNLI, SIS, and I-HOPE) using a two-sided, two-sample, unequal-variance *t* test with overall type I error <0.05 . Three alternative mean changes (standard deviation [SD] of change) in intervention and control populations are 15.3 (SD 22.6) versus 1.3 (SD 23.4) for RNLI, 15.7 (SD 16.1) versus 5.6 (SD 9.1) for the SIS ADL domain, and 62.1 (SD 26.1) versus 46.2 (SD 18.8) for I-HOPE. With a 1:1 allocation ratio, 130 patients (65 in each group) are needed for the RNLI outcome, 84 are needed for the SIS outcome, and 100 are needed for the I-HOPE outcome. We will enroll 180 patients to account for a 30% attrition rate. This magnitude of between-group difference is considered clinically meaningful based on prior relevant literature and is achievable based on our pilot study. Sample size calculation includes correlation between baseline and follow-up measures and is based on analysis of change scores, which is equivalent in efficiency to the proposed analytic model. Based on the number of stroke patient participants, we will enroll an equivalent number of caregivers.

Strengths and Limitations

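### Allocation is balanced on age and FIM as prognostic factors, but the primary model names neither and adjusts for covariates only if a baseline imbalance is seen

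*Combined protocol and SAP*

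**What the plan says.** Under Randomization and Blinding the protocol gives its reason for balancing: "Age is a negative marker for functional recovery after stroke, and functional status is a strong predictor of recovery". It then states: "Randomization will be balanced using the participant's age and FIM score". The assignment is released only "After baseline assessment (T1) is securely uploaded and locked and stratification variables are entered", so both variables are on record before the arm is known.

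The Primary Analysis section fits a linear mixed model to baseline and 12-month RNLI. Its fixed effects are an intercept, time, group and group by time, and β3 (group by 12 months) is the coefficient tested. The one sentence on covariates reads "For improved precision, the model will be adjusted for baseline covariates including race, sex, depression, and length of hospital stay if an imbalance" between arms is found in the baseline analyses. Age and FIM are not on the list. Neither a test nor a cut-off for imbalance is given, and the Baseline Analyses section says its tests are there to "compare T0 and baseline characteristics in the two groups for descriptive information".

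For SIS and I-HOPE, Secondary Analyses says "we will use the same approach as for the primary analysis because these two outcomes are also continuous". That section also plans a functional-impairment-by-group interaction. This is a separate moderator question and does not put FIM in the primary model.

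**The concern.** Four things do not fit together.

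- **Design and analysis disagree.** When allocation is balanced on predictors of the outcome, the treatment estimate varies less from trial to trial. A model that omits those predictors does not credit this, so its standard error overstates the true variability.
- **The trigger does not serve its stated purpose.** Precision depends on how well a covariate predicts the outcome, not on whether it differs between arms by chance. Balancing makes a visible imbalance least likely for age and FIM.
- **The primary model is not fixed in advance.** Whether to adjust, and for what, would be decided after arm-level data are seen, with no stated rule.
- **The form of adjustment is unstated.** Most readers would add covariates as main effects. In a two-visit model that does almost nothing for β3, which is a contrast of changes.

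At stake are some power, needlessly wide intervals and prespecification of the primary test. Inflated type I error is not at stake.

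**Working it through.** **Inputs.** From Sample Size Calculations: RNLI changes of 15.3 against 1.3 (difference 14), SDs of change 22.6 and 23.4, 65 per arm needed, and "We will enroll 180 patients to account for a 30% attrition rate". From Secondary Analyses: alpha 0.016 per endpoint. The R² of age and FIM for 12-month RNLI change is not in the documents; 0, 5, 10 and 20% are assumed.

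**The plan's own figure.** At two-sided alpha 0.016 and 80% power, the unequal-variance t test needs 118 patients, not the stated 130. At 65 per arm, power is 84.6%. The stated figure is thus conservative; this is a separate matter and does not affect what follows. Enrolling 180 and losing 30% leaves 180 × 0.70 = 126, or 63 per arm.

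**Unadjusted test at 63 per arm.** SE0 = √(22.6²/63 + 23.4²/63) = √(1058.32/63) = 4.10. With 124 df the critical value is 2.442 and the noncentrality is 14/4.10 = 3.42, giving power of 83.3%.

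**Effect of R².** Let k = √(1 − R²). Under close balance on the covariates, the unadjusted estimate has true SD k × SE0, but the model reports SE0. Then:

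- unadjusted power = P(noncentral t with 124 df and noncentrality 14/(k·SE0) > 2.442/k)
- actual size = 2·P(t with 124 df > 2.442/k)
- adjusted power uses SE k·SE0 and 2 fewer df
- excess interval width = 1/k − 1

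Example at R² = 10%: k = 0.949, true SD 3.89, effective critical value 2.575, size 0.011.

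| Assumed R² | Unadjusted power | Adjusted power | Gain (points) | Actual size of the 0.016 test | Excess interval width |
|---|---|---|---|---|---|
| 0% | 83.3% | 83.3% | 0 | 0.016 | 0% |
| 5% | 83.9% | 85.4% | 1.5 | 0.0135 | 2.6% |
| 10% | 84.6% | 87.5% | 2.9 | 0.011 | 5.4% |
| 20% | 85.9% | 91.4% | 5.4 | 0.007 | 11.8% |

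Gains are from unrounded values. Simulation with one pair-balanced covariate agrees: power 83.4/84.1/84.5/85.9% unadjusted and 83.4/85.5/87.5/91.3% adjusted, with unadjusted size 0.0157/0.0137/0.0114/0.0071.

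**Does the conditional rule help?** A second simulation used 130 patients, 2 × 2 age-by-FIM strata, blocks of four, the four named covariates explaining a further 10%, and imbalance taken as p < 0.05 (all assumed beyond the 130). At R² of 10/20/30% for age and FIM:

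| Analysis | Type I error | Power |
|---|---|---|
| Unadjusted | 0.011/0.005/0.005 | 86.1/88.7/89.1% |
| Adjusted only on observed imbalance | 0.010/0.006/0.004 | 86.3/88.6/89.4% |
| Always adjusted for age and FIM | 0.015/0.016/0.016 | 88.9/93.3/95.3% |

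The conditional rule behaves like no adjustment. With four independent covariates tested at 0.05, it is triggered in 1 − 0.95⁴ = 18.5% of trials.

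**Main effects or visit interactions?** In participants with both scores, a covariate's main effect cancels from the within-person change, so β3 and its SE do not move. One simulated complete dataset gave an SE of 3.469 without covariates, 3.469 with main effects and 3.270 with covariate-by-visit terms.

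With 180 enrolled and 30% of 12-month scores missing completely at random (400 trials per R²; assumed baseline SD 20, covariates explaining 10% of baseline variance, residual baseline-change correlation −0.4), at R² of 0/5/10/20%:

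- Main effects cut the SE by 0.2/1.1/1.5/2.0% and moved β3 by 0.25 to 0.48 RNLI points on average (at most 2.4).
- Adding the visit interactions cut the SE by 0.4/3.7/6.6/12.2%.

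**The case against.** The strongest reply is that nothing invalid happens. The test is conservative, unadjusted power is at least 83.3% against an 80% target, and the sample size was built on unadjusted change scores. The planned analysis delivers what was planned. That stands; the loss is relative to a better model that costs almost nothing.

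The R² is also unknown and may be near zero. The protocol calls age and functional status predictors of recovery, not of change in self-reported RNLI from shortly after discharge to 12 months, and stable effects on level cancel from β3. This stands too, and is why zero is in the range.

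Close balance is an assumption, because the balancing method is not described in detail. If continuous, normally distributed age and FIM were split at the median (also an assumption), about 64% of the continuous R² would be balanced. For continuous R² of 5/10/20%, adjusting for the split factors would then gain about 0.9/1.9/3.7 points, with size 0.014/0.013/0.010. The table's figures apply to the R² of the factors as used in the allocation.

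If covariates enter as main effects only, the data-dependent trigger moves β3 little. That is fair, but on that reading the stated precision aim is largely unmet.

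Finally, the covariate list opens with a word that leaves room for others. Age and FIM are therefore not excluded. If added, they would still come under the imbalance condition, so this does not answer the point.

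**Conclusion.** The concern holds. It is a point of efficiency and prespecification that should be corrected, not a threat to validity. No section commits age or FIM to the primary model, and the only route to adjustment is an undefined, data-dependent trigger unrelated to prognosis.

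The mismatch between design and model, and the unsettled primary model, follow from the text and need no assumed figure. The size of the loss does: between nothing at R² = 0 and 5.4 power points with intervals 11.8% too wide at R² = 20%, given close balance and 63 evaluable per arm. The 18.5% trigger rate and the attrition results rest on the further assumptions stated with them and are illustrative.

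**What to change.** In the Primary Analysis section, state that age and FIM, in the form used for the allocation, are always included, each with its interaction with visit, and that β3 remains the tested contrast. Apply the same to the SIS and I-HOPE models. Delete the clause that makes adjustment depend on an observed imbalance. If race, sex, depression or length of stay are wanted, name them in advance, enter them in the same way, and use values recorded before randomisation. The timing of the depression scale relative to randomisation is not stated and would need checking first.

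The cost is SAP wording and a few degrees of freedom. No new data are needed, since both allocation variables are entered before the assignment is released. Enrolment is already closed, so the change should be made and dated before anyone analyses outcomes by arm.

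### Replacing the fixed 0.016 tests by Holm's step-down would lift RNLI power from about 83% to 91–92% at the planned effects, within the same family-wise error bound of 0.048

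*Combined protocol and SAP*

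**What the plan says.** The Primary Analysis section makes the 12-month change in RNLI the sole primary comparison. The Secondary Analyses section then adds the one-year changes in SIS and I-HOPE and states: "We have overall type I error control for testing the 1-year change in these three analyses at the design stage". The rule that follows is a single level for each test: "The significance level for testing is 0.016". No step-down, hierarchy or gatekeeping is described anywhere.

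The Sample Size Calculations section says: "The study is designed to have 80% of power to reject three null hypotheses of equal mean changes", with overall two-sided type I error below 0.05. For the primary endpoint the planned mean changes, intervention against control, are "15.3 (SD 22.6) versus 1.3 (SD 23.4) for RNLI". The first of the two secondary endpoints is planned at "15.7 (SD 16.1) versus 5.6 (SD 9.1) for the SIS ADL domain". The entry for the other secondary endpoint reads "62.1 (SD 26.1) versus 46.2 (SD 18.8) for I-HOPE". The section then gives a separate total for each endpoint (130, 84 and 100) and enrols 180 to allow for 30% attrition. It gives no correlation between the three endpoints.

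**The concern.** Three tests at 0.016 are a single-step Bonferroni split: 3 × 0.016 = 0.048. Each endpoint pays the full multiplicity price even when the other two are clearly positive. RNLI pays most, because the primary endpoint has the smallest planned standardised effect of the three.

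In practice, an RNLI p-value between 0.016 and 0.048 would be declared non-significant even with SIS ADL and I-HOPE both convincingly positive. Controlling the family-wise error does not require that outcome.

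**Working it through.** **Inputs.** Differences and SDs of change come from Sample Size Calculations: RNLI 15.3 − 1.3 = 14.0 (SDs 22.6, 23.4); SIS ADL 15.7 − 5.6 = 10.1 (16.1, 9.1); I-HOPE 62.1 − 46.2 = 15.9 (26.1, 18.8). Completers: 180 × 0.70 = 126, taken as 63 per arm (equal attrition is an assumption). Dividing each difference by the root mean square of its two SDs gives standardised effects of 0.61, 0.77 and 0.70.

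**The plan's own figures.** Welch t-test sample sizes for 80% power per endpoint at 0.016 are 118, 76 and 90, not 130, 84 and 100. The stated totals are matched exactly by 85% power at 0.05/3, and also by 80% power at 0.01. The plan states neither setting. The stated totals are therefore larger than 80% per endpoint at 0.016 needs.

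**Power per endpoint at 0.016, 63 per arm.** SE = √((SD₁² + SD₂²)/63); power from the noncentral t with noncentrality difference/SE.

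| Endpoint | SE | Difference/SE | Power |
|---|---|---|---|
| RNLI | √(1058.32/63) = 4.10 | 3.42 | 83.3% |
| SIS ADL | √(342.02/63) = 2.33 | 4.33 | 96.9% |
| I-HOPE | √(1034.65/63) = 4.05 | 3.92 | 92.8% |

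With 130 completers the powers are 84.6%, 97.3% and 93.7%.

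**Holm on the same p-values.** Order the three p-values. Reject the smallest if it is at most 0.048/3 = 0.016, then the next if at most 0.048/2 = 0.024, then the last if at most 0.048, stopping at the first failure.

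- *Error control.* Suppose k nulls are true. When Holm first rejects a true null, at most 3 − k hypotheses have been rejected before it, so its threshold is at most 0.048/k. The chance that any of k true nulls has p ≤ 0.048/k is at most 0.048, whatever the correlation.
- *Dominance.* If m of the p-values are at or below 0.016, they are the m smallest and each meets a threshold of at least 0.016. Holm rejects all of them.

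**RNLI power, 126 completers.** Simulation of three correlated Welch tests, 100,000 trials per setting:

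| True secondary effects | Correlation | Fixed 0.016 | Holm |
|---|---|---|---|
| Both as planned | 0 to 0.8 | 83% | 91–92% |
| Both half of planned | 0 to 0.5 | 83% | 85–86% |
| Both zero | 0 to 0.8 | 83% | 83% |

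In the half-effect row the gain is about 3 points at correlation 0 and about 1 at 0.5; at 0.8 it is only about 0.3. No fixed-rule rejection was lost in any run. With all three nulls true, Holm's simulated family-wise error stayed below 0.048.

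**Power to reject all three at fixed 0.016, planned effects.** The common correlation is an assumption.

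| Completers | 0 | 0.3 | 0.5 | 0.7 |
|---|---|---|---|---|
| 126 (30% attrition) | 74.8% | 76.8% | 78.3% | 80.4% |
| 130 (stated RNLI total) | 77.3% | 78.8% | 80.2% | 82.1% |
| 144 (80% retention, 180 × 0.80) | 83.6% | 84.7% | 85.6% | 86.8% |

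As a check at correlation 0 with 126: 0.833 × 0.969 × 0.928 = 0.749. Holm gives 88–91% in the 126 row over correlations 0 to 0.8.

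**The case against.** **The design meets its power target.** A reader might infer from the wording about rejecting three null hypotheses that the trial misses its 80%. The documents do not support that as a finding. Separate totals of 130, 84 and 100 make sense only if each endpoint was sized on its own, and on that reading all three powers exceed 80%. On the joint reading, a correlation of about 0.5 is enough with 130 completers, and the three instruments overlap in content (self-care, mobility, ADLs). With the 80% retention given under Process Outcomes there is no shortfall at any correlation examined. Part of the gap at 126 comes from the attrition arithmetic (130/0.7 ≈ 186, not 180), not from the 0.016 rule. This objection stands.

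**The gain is conditional.** A reader might also take 8 points as assured. They are not: RNLI is tested at 0.024 only if one secondary endpoint is rejected first, and at 0.048 only if both are. This stands as a limit on size. It does not make Holm worse than the plan in any case.

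**Fixed-sequence testing would protect RNLI better.** Testing RNLI first at 0.048 gives it about 92% power at 126 completers whatever the secondaries do. But it forbids any secondary claim once RNLI fails, so it can lose rejections that the present plan would make. Holm cannot. This is a legitimate alternative preference, not a reason to keep the fixed split.

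**It is late.** Enrolment is closed, and the section on the waiver of consent says that participants have finished the intervention and control programmes. The safety monitoring section provides for review of efficacy outcomes without saying whether that review is blind to arm. Relaxing the primary threshold now invites a credibility challenge. This stands as a condition: the change is defensible only if made, and shown to have been made, before unblinded outcome data are seen.

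**Conclusion.** The point holds as a cheap improvement, not as an error. The fixed 0.016 rule controls the family-wise error but is uniformly dominated by Holm at the same bound. At the planned effects with 126 completers the difference for RNLI is about 8 points, which cuts the chance of missing a true effect of the planned size from about 17% to 8–9%. It shrinks to about 1 to 3 points with half-size secondary effects (correlations 0 to 0.5) and to about zero with none.

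The figures rest on the plan's means and SDs, equal attrition by arm, and change-score t tests, which the plan treats as equivalent in efficiency to its mixed model. The joint-power figures also rest on an assumed correlation. Whether the 80% is per endpoint or joint is an ambiguity to be cleared up; the separate totals favour per endpoint.

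**What to change.** In Secondary Analyses, replace the sentence that sets the 0.016 level by:

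> *The three 12-month tests (RNLI, SIS ADL, I-HOPE) use the Holm step-down procedure with thresholds 0.016, 0.024 and 0.048.*

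In Sample Size Calculations, say whether 80% is per-endpoint power or power to reject all three, and state the significance level and power that produced 130, 84 and 100. If joint power is meant, give the assumed correlation.

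The cost is a short amendment, with no extra patients or data. Simultaneous confidence intervals that match Holm are less simple than the 98.4% intervals that go with the fixed rule; unadjusted intervals could be reported beside the Holm decisions and labelled as such. The amendment should be dated and should record that no one deciding on it had seen outcome data by arm. If that cannot be affirmed, keep 0.016 as the confirmatory rule and report Holm as a supplementary analysis only.
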